#### **5.2.5 Expected Duration of Each Subject's Participation**

The participation duration of each subject is defined as the duration from the time of subject to be enrolled in the trial to the last visit. For each subject, it is estimated that the screening duration is up to 3 days, anticipated treatment i.e. wound bed preparation duration is up to 14 days. In total, expected duration of each subject's participation is up to 17 days. During the period, all patients will have the initial dressing placement and a minimum of 2 dressing changes.

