### **Exploratory endpoints**

Repeated measure analysis of variance using mixed model on mean change in exploratory endpoints (volume, area and granulation tissue) at each dressing change time point as dependent variables with site, treatment group and treatment-by-site interaction as fixed factors, wound size (wounds surface area,  $<15\text{cm}^2$ ,  $15\text{-}30\text{cm}^2$ , and  $>30\text{cm}^2$ ) as covariate, and time point as repeated factor will be performed using mixed model.

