7.6. COMMON CALCULATIONS

For quantitative measurements, change from baseline will be calculated as:

- Test Value at Treatment Interval X – Baseline Value

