7.7. SOFTWARE VERSION

All analyses will be conducted using SAS version 9.2 or higher.

8. Output Presentations

The templates provided with this SAP describe the presentations for this study and therefore the format and content of the summary tables, figures and listings to be provided by Kun Tuo Biostatistics. All data collected will be listed. When the content of this SAP does not match the template, the template will take priority.

9. Disposition and Withdrawals

All subjects who provide informed consent will be accounted for in this study.

The numbers and percentages of subjects who were randomized, completed and discontinued the study early, as well as the reasons for incompletion, will be summarized by site treatment and overall. The numbers and percentages subjects in each analysis set will be provided by treatment group and overall.

Disposition of all subjects will be listed.

10. Protocol Deviations

Any act of intentional or unintentional variation of the protocol is defined as protocol deviation (PD). The information of protocol deviation was recorded on the “protocol deviation” CRF page.

Protocol deviations will be summarized by treatment, categories and overall.

The following information will be reported in Full Analysis Set:

- Frequency and percentage of randomized patients with at least one protocol deviation/violation will be summarized by treatment and overall.
- Protocol deviation will be summarized by grade of deviation, treatment group and overall.
- Detailed information of protocol deviations will be listed, including PPS inclusion/exclusion status.

11. Demographic and other Baseline Characteristics

Demographic data and other baseline characteristics will be presented for Full Analysis Set and the Per Protocol Set.

Demographic data and other baseline characteristics will be summarized by treatment and categories, listing will be provided, including PPS inclusion/exclusion status.

Statistical testing will be carried out for demographic or other baseline characteristics (Fisher's

exact for nominal or ordinal variables, ANOVA for continuous variables).

The following demographic characteristics will be reported for this study:

- Age (years) = (date of consent - date of birth+1)/365.25, and result is rounded down to the nearest integer
- Gender
- Child-bearing potential
- Race
- Ethnicity
- Definitive Surgical Debridement
- Baseline wound area

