15.5. SUMMARIES FOR NPWT APPLICATION

The application time (minutes) for each dressing change, any leaks and treatment settings will be listed and summarized by treatment group.

16. Exploratory endpoints

An exploratory analysis will be conducted on the exploratory endpoints (volume, area and granulation tissue) using the FAS. Listings will be presented and sorted by treatment group, subject id.

Repeated measure analysis of variance using mixed model on mean change in exploratory endpoints(volume, area and granulation tissue) at each dressing change time point as dependent

Analysis Plan

Protocol No.: KCI.VERAFLO.2018.02

variables with center, treatment group and treatment-by-center interaction as fixed factors, wound size (wounds surface area, $<15\text{cm}^2$ (ref), $15\text{-}30\text{cm}^2$, and $>30\text{cm}^2$) as covariate, and time point as repeated factor will be performed using mixed model. The P-value of center, treatment group, treatment-by-center interaction, wound size and time point will be reported. LS Means and LS Mean difference and P-values for LS Mean difference will be reported out for each visit.

Above statistical analysis method will be conducted on wound area.

An example of SAS code is provided:

```
Proc mixed DATA=xxx covtest metood=ml;
Class id treat center woundtype timepoint;
Model volume(or area,or granulation tissue)=treat center treat*center woundtype timepoint
/htype=3 s noint;
Repeated timepoint/type=sample (covariance structure may be TOFL, AR(1) or UN. Likelihood
ratio testing (LRT) may be used to select best fitting model
Subject=id(treat);
Run;
```

17. Evaluation of Safety

All outputs for safety outcomes will be based on safety set, and presented by treatment groups.

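### SAP 16 promises treatment differences for each visit from a model with no treatment-by-time term, so every visit would show the same difference and p-value

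*SAP*

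**What the plan says.** SAP section 16 plans a mixed-model repeated-measures analysis, in the full analysis set, of mean change in volume, area and granulation tissue at each dressing change. Center, treatment group and treatment-by-center are fixed factors, the three-level wound size is a covariate, and time point is the repeated factor.

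- **Promised output.** "LS Means and LS Mean difference and P-values for LS Mean difference will be reported out for each visit".
- **Effects to be given p-values.** "The P-value of center, treatment group, treatment-by-center interaction, wound size and time point will be reported".
- **Example code, right-hand side of the model.** "granulation tissue)=treat center treat*center woundtype timepoint".

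Protocol 6.5.1 (Exploratory endpoints) has the same terms: the outcomes "at each dressing change time point as dependent variables with site, treatment group and treatment-by-site interaction as fixed factors", with wound size as covariate and time point as repeated factor. It does not promise treatment differences by visit.

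SAP section 8 adds a precedence rule: "When the content of this SAP does not match the template, the template will take priority". The templates are not among the documents.

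**The concern.** A difference between arms that may vary from visit to visit needs either a treatment-by-time term or a separate model per visit. SAP 16 specifies neither, yet announces a difference and a p-value for each visit. The omission is not confined to a line of sample code, because the prose and the list of reported effects leave the term out as well.

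At stake is how an exploratory table would be read. If it were laid out by visit and filled from this model, each row would carry the same adjusted difference and p-value. A reader could take that as evidence that the effect is stable over treatment, when stability was imposed by the model. If the arms improve at different rates, the change over time would be missing from the adjusted comparison.

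**Working it through.** The plan gives no figure to reproduce here. The point is one of model structure and follows by algebra from the terms in SAP 16.

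**Step 1: the model as written.** For arm *i* (1 = investigational, 0 = control), center *j* of *J*, wound-size stratum *k* of 3 and time point *t*, the expected outcome is

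μ(i,j,k,t) = m + τ_i + γ_j + (τγ)_ij + ω_k + θ_t

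**Step 2: LS mean for one arm at one visit.** Averaging equally over centers and strata,

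LS(i,t) = m + τ_i + mean_j γ_j + mean_j (τγ)_ij + mean_k ω_k + θ_t

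This changes with *t* through θ_t, so each arm's LS mean can differ between visits.

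**Step 3: difference between arms at visit *t*.**

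LS(1,t) − LS(0,t) = (τ_1 − τ_0) + mean_j [(τγ)_1j − (τγ)_0j]

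θ_t cancels and no term in *t* remains. The same contrast of coefficients applies at every visit, so the estimate, standard error and p-value are the same at every visit. If treatment-by-center is dropped, only τ_1 − τ_0 is left and the conclusion is unchanged. The covariance structure affects what the common value is, but not that it is common.

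**Step 4: with the interaction.** Adding (τθ)_it to the model adds (τθ)_1t − (τθ)_0t to the difference, which can then vary with *t*.

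**Step 5: numerical confirmation on invented data.** One data set was simulated with 128 subjects (the evaluable number in SAP 5.4), and with assumed values for the rest: 5 centers, 3 wound-size strata, 2 to 4 visits per subject, and true differences of 0, 5, 10 and 20 at visits 1 to 4. Both models were fitted by maximum likelihood with a random subject intercept.

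| Visit | Assumed true difference | As written: difference (SE), p | With treatment-by-time: difference (SE), p |
|---|---|---|---|
| 1 | 0 | 3.16 (4.79), 0.509 | 2.19 (5.53), 0.692 |
| 2 | 5 | 3.16 (4.79), 0.509 | −4.49 (5.53), 0.417 |
| 3 | 10 | 3.16 (4.79), 0.509 | 8.72 (6.13), 0.155 |
| 4 | 20 | 3.16 (4.79), 0.509 | 22.91 (7.80), 0.003 |

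The table shows only that the first model repeats itself and the second does not, and that the second has larger standard errors. The values say nothing about this trial.

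**Step 6: how many visits are involved.** Protocol 5.2.5 expects that "all patients will have the initial dressing placement and a minimum of 2 dressing changes". Protocol 5.5.3 gives one change per 48 to 72 hours for up to 14 days (336 hours). Since 336/72 = 4.7 and 336/48 = 7, a subject treated for the full period has four to seven complete intervals. Subjects whose wounds are ready sooner contribute fewer, so later visits contain only those still on treatment.

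**The case against.** **The analysis is exploratory, and by-visit results appear elsewhere.** SAP 15.1.3 describes volume, volume change and percent reduction by visit and arm, and SAP 15.2.3 does so for area. This stands and limits the harm: a diverging pattern would be visible descriptively. Neither section gives the adjusted by-visit comparison that SAP 16 announces.

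**An additive model is legitimate.** This also stands. If the effect is the same at every visit, the single estimate is correct and more precise. The fault is the mismatch between that model and the promised output.

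**The code is only a sketch.** It contains misspellings and no statement requesting LS means, so a programmer would probably notice the gap. That is plausible, and it makes the misleading table less likely. It does not repair the prose or the list of effects, and a repair made after data lock would not be pre-specified.

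**The template may already contain the interaction.** It may, and it has priority. Since it is not available, the conclusion concerns the SAP text and not the eventual output.

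Some stronger readings are tempting but unsupported:

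- *The common value is arbitrary because the covariance structure is open.* The code comment does say that the "covariance structure may be TOFL, AR(1) or UN", but it goes on to name likelihood ratio testing as a way of choosing.
- *The outcome must be absolute change, not percent reduction.* SAP 7.6 says that "change from baseline will be calculated as" visit value minus baseline. But SAP 15.1.3 defines volume change with the opposite sign, and Protocol 6.5.1 and SAP 15.2.3 attach the term mean change to area reduction rates. The wording in SAP 16 is ambiguous and does not settle the scale.
- *The Protocol contradicts itself.* It shares the model but makes no by-visit promise.

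**Conclusion.** The point holds, and it is minor. As written, the SAP 16 model cannot give by-visit treatment differences that vary, so the promised output would be one difference and one p-value repeated at every visit. This follows from the listed terms alone and needs no assumption about the data or the covariance structure. It does assume that the output template does not itself add the interaction or fit separate models by visit.

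The size of any distortion cannot be stated, because the documents contain no by-visit results. It is nil if the effect is constant over visits and grows with the departure from constancy. A reader might infer that the main result is at risk. It is not: the primary endpoint is analysed by a separate ANCOVA on the end-of-treatment reduction rate, and the non-inferiority decision does not use this model.

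**What to change.** In SAP 16:

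1. Add `treat*timepoint` to the model prose, the example code and the list of effects whose p-values are reported.
2. Report the treatment-by-time-point LS mean differences with 95% confidence intervals, labelled as exploratory estimates.
3. State that later visits include only subjects still on treatment, since treatment ends at readiness for closure.
4. Confirm that the output template shows the same model, because it overrides the SAP text.

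No Protocol edit is needed. Protocol 6.6 lets a change of method before data lock be recorded in the SAP, and SAP section 2, which now lists no changes, is the natural place for it.

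The cost is one model term and a few lines of text, using images already planned at each dressing change. The downsides are wider intervals, especially at late visits where fewer subjects remain, and possible bias there because stopping depends on how the wound is doing. If the sponsor does not want that, deleting the by-visit sentence would also make the section consistent, but would give up the comparison it set out to make.

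### The SAP Section 16 example code fits the exploratory repeated-measures model by maximum likelihood with many fixed center terms, so its treatment standard errors come out somewhat too small (minor)

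*SAP*

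**What the plan says.** The Exploratory endpoints part of Protocol 6.5.1 describes a repeated-measures mixed model with "site, treatment group and treatment-by-site interaction as fixed factors", wound-size stratum as covariate, and "time point as repeated factor will be performed using mixed model". It names no estimation method.

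The text of SAP Section 16 repeats this model, with "variables with center, treatment group and treatment-by-center interaction as fixed factors", on the FAS. It has no rule for dropping a non-significant interaction; the primary model in SAP 15.1.3 does have one.

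The estimation method appears only in the Section 16 code, which is introduced as an example:

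- The procedure line is "Proc mixed DATA=xxx covtest metood=ml".
- The model line is "Model volume(or area,or granulation tissue)=treat center treat*center woundtype timepoint", with no RANDOM statement.
- The model options are "htype=3 s noint", so no degrees-of-freedom method is requested.
- The covariance type is printed as `sample`, with a note offering TOFL, AR(1) or UN and adding that likelihood "ratio testing (LRT) may be used to select best fitting model".

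On output, Section 16 states: "The P-value of center, treatment group, treatment-by-center interaction, wound size and time point will be reported". It also promises LS means, LS-mean differences and p-values for those differences at each visit. SAP 7.5 sets the default test level at 5% two-sided.

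**The concern.** ML estimates variances as if the fixed effects were known. REML allows for the parameters estimated. The gap is negligible when fixed effects are few relative to subjects. Here every treatment-by-center cell is a between-subject parameter that is always kept, so the gap grows with the number of centers. The treatment comparison is between subjects, so the shortfall passes into its standard error and p-value.

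The plan gives no reason for ML. Choosing a covariance structure by likelihood ratio does not require it: the candidate models share the same fixed effects, so their REML likelihoods can be compared.

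At stake are the treatment p-values for volume, area and granulation over time. Someone who corrects only the misspelled keyword would leave the bias in place.

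**Working it through.** **Inputs from the documents**
- Estimation method and fixed effects: SAP Section 16.
- Test level: two-sided 5% (SAP 7.5).
- Subjects: at least 140 and up to 170 randomized (Protocol 6.1.1, SAP 5.4). Section 16 uses the FAS, so PPS exclusions do not reduce this number.

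**Assumption**
- Number of centers C: not in the documents as supplied. The 50% cap per site (Protocol 6.1.4.2) implies at least 2. I take 2 to 15.

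**The plan's own figure.** Section 16 states none. The sample size that sets the scale does reproduce. With margin 0.20, SD 0.40 and one-sided 0.025, the normal formula gives 2 × (1.960 + 0.842)² × (0.40/0.20)² = 62.8, so 63 per arm. The exact t calculation gives 80.15% power at the stated 64 per arm.

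**Step 1. Between-subject parameters.** There are 2C treatment-by-center cells plus 2 wound-size terms, so p = 2C + 2.

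**Step 2. Standard-error ratio under a correlated structure.** SE(ML)/SE(REML) ≈ √((n − p)/n).

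**Step 3. Real size of a nominal 5% test.** 2 × P(T > t₀.₉₇₅ × ratio), with T and t₀.₉₇₅ both on n − p degrees of freedom.

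Example with n = 140 and C = 10: p = 22, df = 118, ratio = √(118/140) = 0.918, t₀.₉₇₅ = 1.980, and 1.980 × 0.918 = 1.818. The two-sided tail probability is 7.2%.

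| Centers | p | n = 140: ratio, size | n = 170: ratio, size |
|---|---|---|---|
| 2 | 6 | 0.978, 5.5% | 0.982, 5.4% |
| 5 | 12 | 0.956, 6.1% | 0.964, 5.9% |
| 10 | 22 | 0.918, 7.2% | 0.933, 6.7% |
| 15 | 32 | 0.878, 8.5% | 0.901, 7.7% |

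If only 128 subjects contributed, the size would run from 5.6% (2 centers) to 8.9% (15 centers).

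**Step 4. Simulation check.** ML and REML were fitted to the same data: n = 140, compound symmetry with correlation 0.6, 2 to 6 visits per subject, 2,000 runs for each center count. The same t critical value on n − p df was used for both.

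| Centers | SE ratio | Type I error, ML | Type I error, REML |
|---|---|---|---|
| 2 | 0.978 | 5.4% | 5.0% |
| 5 | 0.956 | 5.6% | 4.7% |
| 10 | 0.917 | 6.4% | 4.5% |
| 15 | 0.877 | 8.5% | 4.8% |

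The Monte Carlo standard error near 5% is √(0.05 × 0.95/2000) = 0.5 percentage points. The simulated SE ratios agree with Step 2 to within 0.001, and REML is close to nominal throughout. A second simulation (10 centers, 5 visits, correlation 0.6, 5,993 trials) gave 7.1% for ML and 5.1% for REML.

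**Step 5. If `sample` means `simple` (independence).** ML then divides by observations rather than subjects. With 140 subjects and an assumed 5 visits there are 700 observations and p = 2C + 2 + 4 parameters. The ratio is √(690/700) = 0.993 at 2 centers and √(664/700) = 0.974 at 15, an understatement of about 1% to 3%. Treating a subject's repeated measurements as independent would then understate the treatment standard error far more than ML does.

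**The case against.** The best reply is that nothing in the trial turns on this model. The analysis is labelled exploratory and the code is labelled an example. The block needs rewriting anyway: the method keyword is misspelled, the covariance names `sample` and `TOFL` are not valid, and there is no treatment-by-timepoint term although differences are promised for each visit. Neither the protocol nor the SAP prose asks for ML. All of this stands and lowers the priority. It does not remove the point, because the code is the only place where an estimation method is stated.

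A reader might infer four stronger things that the documents do not support:

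- **That reported confidence intervals will be too narrow.** Section 16 lists LS means, differences and p-values. Only the general sentence in SAP 7.5 mentions a 95% interval.
- **That the size of the error is known.** It depends on a center count that is not given and on a correlated covariance structure, which the printed code does not clearly request.
- **That the missing degrees-of-freedom option does harm of its own.** The sizes above already use a t reference on n − p df, so all of the inflation shown comes from the ML variance.
- **That the non-inferiority result is affected.** The primary example code (SAP 15.1.3) uses PROC GLM, whose residual variance already divides by n − p. Wound area as a secondary endpoint has its own ANCOVA (SAP 15.2.3).

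**Conclusion.** The point holds as a minor one. The Section 16 code sets ML while always keeping center and treatment-by-center as fixed effects. Under a correlated structure this makes treatment standard errors too small and p-values optimistic. The direction is certain; the size is not.

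For 2 to 15 centers (assumed) and 140 to 170 subjects, standard errors are understated by about 2% to 12%, and the real size of a nominal 5% test is about 5.4% to 8.5%. With few centers the effect is hardly visible. If `sample` means independence, ML costs about 1% to 3% on the standard error and the covariance structure is the bigger problem. Only the exploratory analyses of volume, area and granulation tissue are touched.

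**What to change.** In SAP Section 16:

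1. Replace the method option with `METHOD=REML`. `DDFM=KR` is an optional small-sample refinement.
2. State that covariance structures are compared on the REML likelihood with the fixed effects held the same.
3. Replace `sample` and `TOFL` with a valid correlated default, for example UN, and state a fallback in case it does not converge.

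Make these edits together with the other corrections to the same code, including the missing treatment-by-timepoint term, which is a separate fault and at least as important. The cost is a few words in the SAP and somewhat larger standard errors and p-values in the exploratory tables. No data collection, sample size or primary analysis changes.

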15.1.3. PRIMARY ANALYSIS OF PRIMARY EFFICACY VARIABLES

PPS population is the primary efficacy analysis population. Descriptive statistics of actual wound volume, wound volume changes (wound volume before study treatment –wound volume of each visit) and wound volume reduction rate at visit (wound volume before initial study treatment –wound volume at visit)÷wound volume before initial study treatment×100% by visits, treatment group and overall will be provided.

Listings of actual wound volume will be presented and sorted by subject id, treatment group and visit.

The statistical hypothesis for testing the treatment group difference for primary efficacy endpoint is presented as follows:

- $H_0: M_T - M_C \leq -0.20$ tested against the alternative hypothesis
- $H_1: M_T - M_C > -0.20$

where:

M_C is the means in control group and M_T is the means in to V.A.C. VERAFLTM group.

A two-sided 95% confidence interval for $M_T - M_C$ will be constructed using the method of ANCOVA with treatment group, center, and treatment-by-center interaction (if the interaction effect is not statistically significant, then it will be removed from the final model) as fixed factors, and wound size (wounds surface area, <15cm² (ref) , 15-30cm², and >30cm²) as covariate.

The following statistics will be presented: LS Means, difference of the LS Means as well as its two-sided 95% CI, p-value for LS Mean difference. If the lower limit of the two-sided 95% confidence interval of difference is greater than -0.20, then it will be concluded that the V.A.C. VeraFloTM Dressing Kit is non-inferior to the approved control dressing in China (Local) + wall suction.

A rejection of the null hypothesis will trigger superiority testing based upon treatment difference. If the lower limit of the CI is greater than zero, V.A.C. VERAFLTM Dressing Kit is proven to be superior to control dressing.

The two hypothesis tests are hierarchically structured so that the second test (superiority) will only be considered if the first test (non-inferiority) is rejected. There is no alpha adjustment for the second test

as a result of the hierarchical testing.

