Furthermore, the following statistics will be presented: P-value of treatment group, center, wound size, and treatment-by-center interaction (present only if interaction effect is significant). If the treatment-by-center interaction in ANCOVA model is significant (<0.025), it always reveals that there is the heterogeneity of substantial treatment in different centers. In order to explain the heterogeneity influence for reliability of statistical conclusion, the descriptive statistics will be reported by different centers.

An example of SAS code is provided:

```
Proc glm;
Class treat woundtypecenter;
Model wound volume reduction rate=treat center treat*center woundtype/ss3;
Lsmean treat/cl pdiff tdiff;
run;
```

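### The SAP 16 example code models raw wound size where the protocol and SAP text specify change; no continuous baseline value is in the model, and change has two opposite signs

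*SAP*

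**What the plan says.** **Outcome in the text.** Protocol 6.5.1 (Exploratory endpoints) plans a "Repeated measure analysis of variance using mixed model on mean change in exploratory endpoints (volume, area and granulation tissue") at each dressing change. SAP 16 repeats this almost word for word: "Repeated measure analysis of variance using mixed model on mean change in exploratory endpoints(volume, area and granulation tissue"). SAP 2 declares no change from the protocol.

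**Outcome in the code.** SAP 16 then says "An example of SAS code is provided" and gives the model line "Model volume(or area,or granulation tissue)=treat center treat*center woundtype timepoint".

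**Size terms.** Text and code carry one: the wound surface-area class (<15, 15-30, >30 cm²). The code calls it `woundtype`; I read it as the area class because it stands where the text has wound size. The same class is the randomisation stratum (protocol 5.5.2.2). Continuous baseline volume or area appears in neither.

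**Meaning of change.** SAP 7.6 defines it for quantitative measurements as "Test Value at Treatment Interval X – Baseline Value". SAP 15.1.3 describes "wound volume changes (wound volume before study treatment –wound volume of each visit"), the opposite order, and SAP 15.2.3 does the same for area. SAP 16 gives no definition of its own.

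**Required output.** SAP 16 asks for LS means, their differences and p-values at each visit.

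**The concern.** A programmer who follows the text and one who follows the code would analyse different outcomes. The second would compare wound sizes, adjusted only for a coarse class that is open-ended above 30 cm² and does not measure depth or volume. Differences in starting size within a class then go into the error term, and any chance imbalance in starting size goes into the treatment difference. The likely costs are a less precise exploratory comparison and a choice of outcome left open until data are in hand.

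The sign conflict adds a reading risk. With baseline minus visit, a positive difference favours the investigational arm; with visit minus baseline, it favours the control.

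**Working it through.** **1. Is the coded outcome just shorthand for change?** The primary-endpoint code in SAP 15.1.3 writes out its derived outcome: "Model wound volume reduction rate=treat center treat*center woundtype/ss3". The SAP 16 code names only the measures. Shorthand is possible, but nothing in SAP 16 says so.

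**2. The plan's own figure.** The documents give no precision or power figure for this analysis. The primary sizing reproduces (margin 20%, SD 40%, one-sided 0.025: power 79.5% at 63 per arm and 80.1% at 64), but it does not bear on this point.

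**3. Precision at one visit.** Let B be baseline size and Y = B(1 − R) the size at a visit. R is the proportional reduction, with mean r and SD s, independent of B. Let k be the variance of B left within area classes, divided by the mean of B². With the area class in every model, the residual variances are proportional to:
- raw Y: (1 − r)²k + s²
- change B − Y: r²k + s²
- either outcome with continuous B added: s²

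Hence:
- SE ratio, raw / with baseline = √[1 + (1 − r)²k/s²], which always exceeds 1 while k > 0 and r < 1.
- SE ratio, raw / change alone = √{[(1 − r)²k + s²]/[r²k + s²]}, which falls below 1 once r exceeds 0.5.
- Baseline share of the raw residual variance = (1 − r)²k/[(1 − r)²k + s²].

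**4. Inputs.** Only s = 40% comes from the documents (the planning SD of the reduction rate, SAP 5.4). The rest is assumed: roughly lognormal area with median 20-40 cm² and log-SD 0.5-1.0, variable depth, r = 10-60%, s = 15-40%.

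**5. One case by hand.** Take median area 25 cm² and log-SD 0.7. Volume then has CV 0.93, and the area class explains 35% of its variance. So k = 0.93² × 0.65/(1 + 0.93²) = 0.562/1.865 = 0.301.
- r = 0.10, s = 0.15: √(1 + 0.81 × 0.301/0.0225) = √11.84 = 3.44
- r = 0.40, s = 0.40: √(1 + 0.36 × 0.301/0.16) = √1.68 = 1.30
- r = 0.60, s = 0.40: √(1 + 0.16 × 0.301/0.16) = √1.301 = 1.14

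Simulation with 400,000 wounds gave 3.44, 1.28 and 1.14.

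**6. Simulated range over the assumed distributions.**

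| Visit | Measure | Raw / with baseline | Raw / change alone |
|---|---|---|---|
| r 10%, s 15% | area | 1.8-3.7 | 1.7-3.4 |
| r 10%, s 15% | volume | 2.9-4.1 | 2.7-3.8 |
| r 30-40%, s 40% | area | 1.06-1.43 | 1.03-1.31 |
| r 30-40%, s 40% | volume | 1.20-1.52 | 1.10-1.36 |
| r 60%, s 25-40% | both | 1.03-1.45 | 0.78-0.96 |

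The baseline share of the raw residual variance is 67-94% in the early-visit case, 12-56% at 30-40% reduction and 5-53% at 60%. The area class explains 31-73% of baseline area variance but only 23-41% of baseline volume variance, so volume loses more.

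**7. Per-visit output.** The code has treatment, centre, their interaction, `woundtype` and `timepoint`, but no `treat*timepoint` term and no LSMEANS statement. The treatment effect is therefore held constant over visits, and the per-visit differences that the text asks for cannot come from this code.

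**The case against.** The strongest reply is that the plan is already clear. Protocol and SAP text agree on mean change. The conflicting block is labelled an example and is visibly pseudo-code: it contains misspelled options, and its left-hand side lists three alternatives. SAP 8 also gives the output templates, which are not shown, priority over the SAP. The protocol's own model has no continuous baseline, so adding one goes beyond aligning code with text. On sign, SAP 7.6 is the general rule, while 15.1.3 and 15.2.3 define change locally for descriptive tables. All of this stands, and it limits the point to a minor one. It does not remove it: the primary code does spell out its derived outcome, and two sign conventions for the same wound measures remain.

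A reader might go further and infer that the model has no baseline adjustment at all, that it mostly compares starting wound sizes, or that it generally loses much of its precision. The documents do not support this. The area class is a baseline size term, though a coarse one. Allocation is randomised and stratified on it, so leftover baseline size is noise and chance imbalance, not systematic bias. In the calculations its share is a clear majority at early visits and mostly below half later. Nor is change on its own always the better outcome: at 60% mean reduction, raw size was the more precise of the two.

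**Conclusion.** The point holds as a minor inconsistency with an inexpensive gain in precision. The text specifies change and the example code specifies raw size; no continuous baseline value is in either; and change has two signs. Following the code would give a standard error about 1.03 to 4.1 times that of a model with the continuous baseline. At the planning SD of 40% with a 30-40% reduction, the factor is 1.06-1.52, equivalent to the information from about 89% (1/1.06²) down to 43% (1/1.52²) of the subjects.

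These figures rest on assumed wound-size distributions and on reduction being independent of baseline size. They cover one visit at a time, without site effects or repeated-measures correlation, and granulation tissue was not examined. The analysis is exploratory, on the FAS, and plays no part in the non-inferiority decision.

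**What to change.** In SAP 16:
- Make the coded dependent variable the change from baseline, as the protocol and SAP text say.
- Add the continuous baseline value of the same measure as a covariate in both text and code, and keep the area class. Do not move to change without this covariate, because that can lose precision when reductions are large. With the same baseline in the model, raw and change outcomes give the same treatment difference apart from sign.
- State one sign for volume and area change and use it throughout, for example baseline minus visit with positive meaning reduction, as an explicit exception to SAP 7.6.
- Add `treat*timepoint` and an LSMEANS statement so that the per-visit differences can be produced.
- Check that the output templates match, since SAP 8 gives them priority.

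The cost is a few lines of SAP wording and code. Baseline volume and area are already collected, so no new data are needed.
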